4.1.2 Preclinical and Clinical Trial Data

Refer to the Investigator's Brochure for Preclinical and Clinical data.

4.2 Rationale

4.2.1 Rationale for the Trial and Selected Subject Population

Metastatic squamous cell carcinomas (SCC) and adenocarcinomas of the esophagus, stomach, and gastroesophageal junction (GEJ) account for a high proportion of worldwide cancer-related mortality. While some progress has been made for HER2 and VEGFR2 targeted therapies in adenocarcinomas,^{1,2} options for metastatic SCC remain dismal. Evidence for cytotoxic agents in SCC typically stem from a small proportion of patients enrolled in large phase III trials predominated by patients with adenocarcinoma histologies.³ Novel targeted therapeutic approaches for both subtypes are desperately needed.

Pembrolizumab has demonstrated encouraging preliminary evidence of activity in small cohorts of gastric and esophageal cancer patients within the KEYNOTE-012 and KEYNOTE-028 trials, respectively.^{4,5} Both trials selected for patients with evidence of PD-L1 expression within tumor stroma and/or tumor cells. KEYNOTE-012 reported a 22.2% overall response rate by central review, while KEYNOTE-028 noted a 30.4% overall response rate when assessed by investigator review. The activity of pembrolizumab in gastroesophageal cancer patients without tumor PD-L1 expression remains unknown, though lack of PD-L1 expression does not necessarily translate to an absolute lack of response to immune checkpoint inhibitors in pooled analyses of patients with melanoma, NSCLC, and genitourinary malignancies.⁶ Given the promising early evidence of clinical efficacy in gastroesophageal cancers, strategies should be further developed to enhance the potency of immune checkpoint inhibitors, even in patients whose tumors are currently not considered to have detectable PD-L1 expression.

The abscopal effect is a rarely observed though well annotated clinical phenomenon in cancer radiotherapy (RT), in which non-irradiated metastatic lesions distant from the primary tumor site directly subjected to radiation are noted to regress. This phenomenon has been attributed to immune-mediated effects in preclinical models,⁷ and provides rationale that immune checkpoint inhibition and RT could act synergistically. In a recent preclinical study, PD-1 was reported to suppress RT antitumor response, though delivery of a PD-1 blocking antibody

enhanced antitumor response at the primary radiated site as well as non-irradiated metastatic lesions.⁸ Furthermore, radiation therapy has been shown to drive up the expression of PD-L1 tumor expression in preclinical models.^{8,9,10} Mounting evidence also supports that mutational load in tumors correlate with clinical benefit from immune checkpoint inhibition.¹¹ Results from The Cancer Genome Atlas (TCGA) have demonstrated both esophageal SCC and gastric adenocarcinomas demonstrate a high rate of somatic mutations.^{12,13} Furthermore, the development of esophageal SCC is commonly attributed to tobacco smoking, a risk factor shared with NSCLC in which anti-PD-1 strategies have been successful. It is not uncommon for patients with metastatic disease to undergo palliative, traditional external beam multifractionated RT to their primary tumor for the treatment of dysphagia, pain, or gastrointestinal bleeding or a single metastatic site such as a bone metastasis for the treatment of pain. The concordant delivery of pembrolizumab during palliative RT thus serves as an attractive window-of-opportunity trial to determine if the abscopal effect may be augmented with immune checkpoint blockade.

We propose a prospective trial to assess pre- and post-treatment biopsies of patients' metastatic sites with the hypothesis that tumor cytotoxic T cells will be increased with combining pembrolizumab and palliative RT with corresponding improvement in clinical activity. As we will only be radiating a single target lesion in this study population, assessment of response among non-irradiated metastatic sites will serve as a true measure of the abscopal effect. Toxicities are not anticipated to be overlapping for these two modalities, though safety should still be assessed in this early cohort of patients to ensure immune-mediated or radiation-induced toxicities are not exacerbated by the combination. At City of Hope where patients will be solely recruited for this trial, we have extensive experience in the conduct of pre- and post-treatment biopsy studies having completed accrual to a pilot trial of the novel nanopharmaceutical CRLX101 in this disease subset (Clinicaltrials.gov, NCT01612546). We also have a broad gastroesophageal cancer patient population evaluating more than 60 new cases per year due to our institution serving the diverse, multicultural population of the San Gabriel Valley in Los Angeles County. [name], MD, Chair of the Department of Immuno-Oncology, will serve as a collaborating investigator on this study given his laboratory's expertise in translational analyses of tumor/immune/stromal cell interactions.

4.2.2 Rationale for Dose Selection/Regimen/Modification

An open-label Phase I trial (Protocol 001) is being conducted to evaluate the safety and clinical activity of single agent MK-3475. The dose escalation portion of this trial evaluated three dose levels, 1 mg/kg, 3 mg/kg, and 10 mg/kg, administered every 2 weeks (Q2W) in subjects with advanced solid tumors. All three dose levels were well tolerated and no dose-limiting toxicities were observed. This first in human study of MK-3475 showed evidence of target engagement and objective evidence of tumor size reduction at all dose levels (1 mg/kg, 3 mg/kg and 10 mg/kg Q2W). No MTD has been identified to date. 10.0 mg/kg Q2W, the highest dose tested in PN001, will be the dose and schedule utilized in Cohorts A, B, C and D of this protocol to test for initial tumor activity. Recent data from other clinical studies within the MK-3475 program has shown that a lower dose of MK-3475 and a less frequent schedule may be sufficient for target engagement and clinical activity.

PK data analysis of MK-3475 administered Q2W and Q3W showed slow systemic clearance, limited volume of distribution, and a long half-life (refer to IB). Pharmacodynamic data (IL-2 release assay) suggested that peripheral target engagement is durable (>21 days). This early PK and pharmacodynamic data provides scientific rationale for testing a Q2W and Q3W dosing schedule.

A population pharmacokinetic analysis has been performed using serum concentration time data from 476 patients. Within the resulting population PK model, clearance and volume parameters of MK-3475 were found to be dependent on body weight. The relationship between clearance and body weight, with an allometric exponent of 0.59, is within the range observed for other antibodies and would support both body weight normalized dosing or a fixed dose across all body weights. MK-3475 has been found to have a wide therapeutic range based on the melanoma indication. The differences in exposure for a 200 mg fixed dose regimen relative to a 2 mg/kg Q3W body weight based regimen are anticipated to remain well within the established exposure margins of 0.5 – 5.0 for MK-3475 in the melanoma indication. The exposure margins are based on the notion of similar efficacy and safety in melanoma at 10 mg/kg Q3W vs. the proposed dose regimen of 2 mg/kg Q3W (i.e. 5-fold higher dose and exposure). The population PK evaluation revealed that there was no significant impact of tumor burden on exposure. In addition, exposure was similar between the NSCLC and melanoma indications. Therefore, there are no anticipated changes in exposure between different indication settings.

The rationale for further exploration of 2 mg/kg and comparable doses of pembrolizumab in solid tumors is based on: 1) similar efficacy and safety of pembrolizumab when dosed at either 2 mg/kg or 10 mg/kg Q3W in melanoma patients, 2) the flat exposure-response relationships of pembrolizumab for both efficacy and safety in the dose ranges of 2 mg/kg Q3W to 10 mg/kg Q3W, 3) the lack of effect of tumor burden or indication on distribution behavior of pembrolizumab (as assessed by the population PK model) and 4) the assumption that the dynamics of pembrolizumab target engagement will not vary meaningfully with tumor type.

The choice of the 200 mg Q3W as an appropriate dose for the switch to fixed dosing is based on simulations performed using the population PK model of pembrolizumab showing that the fixed dose of 200 mg every 3 weeks will provide exposures that 1) are optimally consistent with those obtained with the 2 mg/kg dose every 3 weeks, 2) will maintain individual patient exposures in the exposure range established in melanoma as associated with maximal efficacy response and 3) will maintain individual patients exposure in the exposure range established in melanoma that are well tolerated and safe.

A fixed dose regimen will simplify the dosing regimen to be more convenient for physicians and to reduce potential for dosing errors. A fixed dosing scheme will also reduce complexity in the logistical chain at treatment facilities and reduce wastage.

4.2.3 Rationale for Endpoints

4.2.3.1 Efficacy Endpoints

The clinical efficacy of combining pembrolizumab and palliative radiotherapy will be measured by assessing overall response rate by RECIST 1.1 and irRECIST. To truly measure the abscopal effect, patients will be required to have metastatic disease sites outside the field of palliative radiation that are considered measurable by RECIST 1.1.

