3.2 Secondary Objective(s) & Hypothesis(es)

(1) **Objective:** To establish that the combination of pembrolizumab and RT is feasible in this patient population and evaluate toxicities per NCI CTCAE ver.4.03.

Hypothesis: The combination of pembrolizumab and RT will be feasible with an acceptable safety profile to warrant future studies.

(2) **Objective:** To evaluate overall response rate (ORR) per RECIST1.1 and irRECIST in this treatment population and correlate with tumor T-cell response.

Hypothesis: The combination of pembrolizumab and RT will demonstrate clinical efficacy with a promising response rate compared to historical controls to warrant future studies.

(3) **Objective:** To evaluate progression-free (PFS) and overall survival (OS) in this treatment population.

Hypothesis: The combination of pembrolizumab and RT will demonstrate promising PFS and OS to warrant future studies.

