5.1.1 Inclusion Criteria

Participants must meet all of the following criteria on screening examination to be eligible to participate in the study:

Patient MRN:

Patient Initials: (F,M,L):

Informed Consent and Willingness to Participate

- 1. Documented informed consent of the participant
- 2. Willing to provide tumor tissue amenable to ultrasound or CT-guided biopsy for biomarker analyses.
 - Patients with malignant ascites are permitted to participate and provide ascites samples for biomarker analyses.
 - Patients receiving radiation to a single metastatic site in which only the primary tumor is accessible for biopsy by endoscopy will also be eligible.

Age Criteria, Performance Status and Life Expectancy

- 3. Age: ≥ 18 years
- 4. ECOG performance status of ≤ 1
- 5. Life expectancy of ≥ 3 months

Nature of Illness and Treatment History

- 6. Diagnosis of metastatic squamous cell carcinoma and/or adenocarcinoma of the esophagus, gastroesophageal junction, or stomach in need of palliative radiotherapy to the primary tumor or a single metastatic site for symptoms such as pain, dysphagia, and/or gastrointestinal bleeding.
 - Patients with adenocarcinoma histology and known HER2-overexpressing disease are permitted to participate if they progressed or are intolerant of prior trastuzumab-containing therapy.

- ___ 7. Measurable metastatic sites of disease outside of the target lesion undergoing palliative radiation based on RECIST 1.1 as assessed by the investigator.
- ___ 8. Have no limits on prior lines of therapy or may be treatment-naïve if in need of palliative RT provided the patient has not received prior anti-PD-1, anti-PD-L1, or anti-PD-L2 therapy.

Laboratory Criteria (within 10 days of treatment initiation unless indicated otherwise)

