5.3.2 Prohibited Concomitant Medications

Subjects are prohibited from receiving the following therapies during the Screening and Treatment Phase (including retreatment for post-complete response relapse) of this trial:

- Antineoplastic systemic chemotherapy or biological therapy
- Immunotherapy not specified in this protocol
- Chemotherapy not specified in this protocol
- Investigational agents other than pembrolizumab
- Radiation therapy outside of the clinical target volume of the index target lesion
 - Note: Radiation therapy to a symptomatic lesion other than the index target lesion or to the brain may be allowed at the investigator's discretion if the radiation course occurs after radiation has completed to the index target lesion.
- Live vaccines within 30 days prior to the first dose of trial treatment and while participating in the trial. Examples of live vaccines include, but are not limited to, the following: measles, mumps, rubella, varicella/zoster, yellow fever, rabies, BCG, and typhoid vaccine.

- Systemic glucocorticoids for any purpose other than to modulate symptoms from an event of clinical interest of suspected immunologic etiology. The use of physiologic doses of corticosteroids may be approved after consultation with the Sponsor.

Subjects who, in the assessment by the investigator, require the use of any of the aforementioned treatments for clinical management should be removed from the trial. Subjects may receive other medications that the investigator deems to be medically necessary.

The Exclusion Criteria describes other medications which are prohibited in this trial.

There are no prohibited therapies during the Post-Treatment Follow-up Phase.

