9.0 STATISTICAL ANALYSIS PLAN

9.1 Primary Objective

The primary objective of this study is to establish that the combination of pembrolizumab and a palliative course of traditional external beam multifractionated RT in patients with metastatic gastric, esophageal, and/or GEJ cancers will lead to an increase in tumor infiltrating cytotoxic T-cells and circulating cytotoxic T cells and a reduction in immunosuppressive Tregs and MDSCs in non-irradiated sites.

Each patient will serve as their own control, and tumor cytotoxic T cell infiltration and immunosuppressive Tregs will be compared pre- and post-treatment. As variability of the difference in the T cell populations pre- and post-treatment is unknown and still being established, the power calculation is based on the concept of “effect size” in this biomarker analysis study. Specifically, a sample-size of 14 patients will have 80% power to detect an effect size of 0.71 using a paired t-test with a 0.05 one-sided significance level. The effect size is the mean difference divided by the standard deviation of the difference.

A positive biological signal combined with acceptable secondary endpoints (response and toxicity) are sought for a clear indication of promise of this combination.

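### The rationale names response outside the radiation field as the measure of the abscopal effect, but the plan defines only overall ORR and gives no rule for irradiated lesions

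*Combined protocol and SAP*

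**What the plan says.** **Aim and measure.** Section 4.2.1 describes a "window-of-opportunity trial to determine if the abscopal effect may be augmented with immune checkpoint blockade". It then names the measure: because only one lesion is irradiated, "assessment of response among non-irradiated metastatic sites will serve as a true measure of the abscopal effect".

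**What follows from that.** The provision made is at entry. Inclusion criterion 7 (5.1.1) asks for "Measurable metastatic sites of disease outside of the target lesion undergoing palliative radiation", and 4.2.3.1 gives measuring the abscopal effect as the reason for this requirement.

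**The response endpoint.** Section 4.2.3.1 says that "The clinical efficacy of combining pembrolizumab and palliative radiotherapy will be measured by assessing overall response rate by RECIST 1.1 and irRECIST". Section 3.2 sets ORR as a secondary objective "in this treatment population and correlate with tumor T-cell response". Section 9.2 lists ORR as exploratory and attaches one figure to it: a 96% chance of at least one responder among 14 patients at a true rate of 21%.

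**Lesion rules.** Section 7.1.2.6.1 asks staff to confirm at least one RECIST target lesion and does not say that it must lie outside the field. Section 7.1.2.6.2 and Table 4 cover scan timing, confirmation and treatment after progression. Appendix 2 adopts RECIST 1.1 and irRECIST by citation.

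**Later radiotherapy.** Section 5.3.2 notes that "Radiation therapy to a symptomatic lesion other than the index target lesion or to the brain may be allowed" once the index course is complete. It gives no scoring consequence.

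**The concern.** The measure promised in 4.2.1 has no endpoint. The entry rule ensures that out-of-field lesions exist at baseline, but nothing says that they will be scored or reported separately.

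The plan also leaves open whether the irradiated lesion can be one of the RECIST target lesions. The wording adds to the doubt: in 5.1.1 and 5.3.2 *target lesion* means the irradiated lesion, while in 7.1.2.6.1 it means a measurable RECIST lesion.

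If the irradiated lesion is measurable and enters the sum, two readings suffer:

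- **The abscopal reading.** A response may reflect local shrinkage, or a real out-of-field response may be masked by an irradiated lesion that does not shrink.
- **The correlation with T-cell response planned in 3.2.** Section 9.1 places the biology out of field ("reduction in immunosuppressive Tregs and MDSCs in non-irradiated sites"), while the response variable paired with it could be driven by the irradiated lesion.

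The trial is open-label with 14 patients. One reclassified patient moves ORR by 1/14, about 7 percentage points, so the scoring rule should be fixed before scans are read.

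**Working it through.** **1. The plan's own figure (9.2).** P(at least one responder in 14) = 1 − (1 − p)^14. At p = 0.21 this is 1 − 0.79^14 = 1 − 0.0369 = 0.963, so the stated 96% reproduces. It refers to overall ORR.

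**2. Where out-of-field response is dealt with.**

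| Section | Content | Out-of-field response defined? |
|---|---|---|
| 4.2.1 | Named as the measure of the abscopal effect | Named only |
| 4.2.3.1, 5.1.1 | Measurable out-of-field disease required | Entry condition only |
| 3.2, 4.2.3.1, 9.2 | Overall ORR | No |
| 7.1.2.6.1, 7.1.2.6.2, Table 4 | Baseline check, scan timing, handling of progression | No |
| 9.1 | Non-irradiated sites, for immune cells | Not for radiologic response |

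**3. How pooling could mislead (illustration).** The documents give no lesion sizes, so these are assumed. Let w be the irradiated share of the baseline sum. Then pooled fall = w × (in-field fall) + (1 − w) × (out-of-field fall).

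- 60 mm irradiated halves, 40 mm outside unchanged: (30 + 40)/100 = 0.70. Pooled fall 30%, out-of-field fall 0%.
- 60 mm irradiated unchanged, 40 mm outside halves: (60 + 20)/100 = 0.80. Pooled fall 20%, out-of-field fall 50%.

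If partial response means a 30% fall (an assumption, since the documents do not reproduce the threshold), the first patient responds and the second does not.

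| Irradiated share w | Only irradiated lesion halves: 0.5w | Only out-of-field lesions halve: 0.5(1 − w) | In-field fall needed for a 30% pooled fall, nothing outside: 0.30/w |
|---|---|---|---|
| 40% | 20% | 30% | 75% |
| 50% | 25% | 25% | 60% |
| 60% | 30% | 20% | 50% |

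At a share of 30% the irradiated lesion would have to vanish (0.30/0.30 = 100%). Below that share it cannot produce a 30% pooled fall alone. The problem therefore depends on the share and is not automatic.

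**4. Reach of the 96%.** No out-of-field rate is given. For assumed rates of 5%, 10% and 15%, the chance of at least one out-of-field responder in 14 is 51%, 77% and 90%. The 96% carries over only if the out-of-field rate is also about 21%.

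**5. Limit of any out-of-field rate in one arm.** Section 4.2.1 reports that "KEYNOTE-012 reported a 22.2% overall response rate by central review, while KEYNOTE-028 noted a 30.4% overall response rate", both in PD-L1-selected patients given pembrolizumab. If those rates applied out of field here (an assumption), at least one responder in 14 would appear with probability 1 − 0.778^14 = 0.970 or 1 − 0.696^14 = 0.994, with no abscopal effect at all.

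**6. Precision.** At 21%, about 0.21 × 14 = 2.9 responders are expected. For 3 of 14 the exact (Clopper-Pearson) 95% interval is 5% to 51%.

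**The case against.** **RECIST may already settle it.** Both criteria are adopted by citation, and a rule on irradiated lesions could sit in those sources. This stands as a limit: a reader might infer that no scoring rule exists anywhere, and the documents cannot show that. But a rule on target-lesion selection for overall ORR would not by itself create the separate measure named in 4.2.1.

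**The abscopal effect is rationale, not an objective.** It appears in section 4 and in none of the objectives in section 3. This stands and lowers the weight of the point. The correlation of response with T-cell response is, however, a stated secondary objective. Section 9.2 gives no method for it, and with about three responders it will be imprecise under either definition.

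**A single arm cannot isolate the effect anyway.** Correct, as step 5 shows. A separate out-of-field rate removes the in-field confound and no more, so the claim in 4.2.1 needs softening as well.

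**The example is chosen to show harm.** Partly fair: at shares of 40% or 50%, halving only the irradiated lesion gives no response under the assumed threshold.

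**Stronger readings to resist.** A reader might infer that overall ORR is invalid or inflated, or that the combination can no longer be judged. The documents support neither. Overall ORR remains a legitimate measure of the combined treatment, the error could run either way, and the judgement in 9.1 and 9.2 can rest on it.

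**Conclusion.** The point holds as a definition gap. The plan names response in non-irradiated sites as its measure of the abscopal effect, requires the lesions needed to assess it, and then defines only overall ORR with no stated rule for irradiated lesions.

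The harm is conditional. It arises only if the irradiated lesion is measurable and enters the sum, and its size and direction cannot be derived from the documents. It reaches the abscopal interpretation and the T-cell correlation, both resting on an exploratory endpoint. The primary paired comparison and its power are untouched, and the 96% is correct for the overall rate to which it refers. This is a cheap improvement, not a flaw that undermines the trial.

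**What to change.** In 7.1.2.6.1 and 9.2:

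- **Overall ORR.** State whether the irradiated index lesion may be a target lesion, and state the denominator; 9.2 defines a population only for safety.
- **Out-of-field ORR.** Add it as a descriptive endpoint in the same patients, with target lesions chosen only outside the radiation field. New lesions, and progression of non-measurable out-of-field disease, still count against response. Report an exact 95% interval, and use this rate for the abscopal interpretation and the T-cell correlation.
- **Lesions irradiated later under 5.3.2.** Count toward out-of-field response only responses documented before that radiotherapy, with no special floor on the diameter. This concerns scoring only, not whether such radiotherapy is permitted.
- **The zero-of-14 statement.** Keep it on overall ORR, and note that its 96% carries over only if the out-of-field rate is also about 21%.

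In 4.2.1, soften the claim about what non-irradiated response measures, and say that a single arm cannot separate an abscopal effect from pembrolizumab's own systemic activity.

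**Cost.** Some wording and one lesion-level data item (inside or outside the field, with the date of any irradiation). The lesions are required at entry and the scans are already scheduled, so no patient or scan is added. The downside is a second exploratory response rate that is imprecise at 14 patients and less comparable with historical ORR.
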